### **13.5.2 Accrual monitoring stopping rule**

The study design assumes that 1-2 patients will accrue per month to each cohort, leading to a 1 to 2 year total accrual period (including leading time for sites to open the studies). At 12 months, if the total accrual is below 25% of the expected (fewer than 8 patients) the study team will evaluate with the scientific question will be of interest at the completion of the accrual period. If it is deemed that the scientific question is likely not to have relevance at the end of the projected accrual period, the study may close. Otherwise, the study team will continue to boost the accrual rates. The accrual rate will be checked every subsequent 6 months and the likelihood that the study questions will still be of interest at the end of the trial will be evaluated and based on this, a decision will be made whether or not to continue accrual to the study.

### **13.5.3 Imaging concordance: image consistency monitoring rule**

After the first 10 patients are enrolled across two arms (i.e., regardless of arm) and who have received at least one dose of BRAF and MEK inhibitors and contrast enhanced MRI performed per protocol, if one out of the first 10 patients, or if at any time after the first 10 patients are enrolled, 10% or more patients are deemed having progressive disease per local bidimensional assessment but are not confirmed by central review assessment, then the study team will review with CTEP regarding implementation of real time central review of imaging in the remaining patients.

## **13.6 Study reporting**

**13.6.1** This study will be monitored by the study team on a monthly basis upon enrollment of the first patient. Reports containing a summary of adverse events by treatment arm will be reviewed. The study team will also monitor the accrual rate.

**13.6.2** This study will be monitored by the Clinical Data Update System (CDUS) version 3.0. Cumulative protocol and patient-specific CDUS data will be submitted electronically to CTEP on a quarterly basis, either by FTP burst of data or via the CDS web application. Reports are due January 31, April 30, July 31, and October 31. Instructions for submitting

data using the CDUS can be found on the CTEP Web site

Note: This study has been assigned to CDUS-Abbreviated reporting, no adverse events (routine or expedited) is required to be reported via CDUS.

**13.6.3** This study will be monitored by the Food and Drug Administration due to the Investigational New Drug (IND) status of the agent. An IND report will be produced and submitted to the Regulatory Affairs Manager within 60 days of the anniversary date that the IND went into effect.

**13.6.4** Results reporting on Clinicaltrials.gov: At study activation, this study will have been registered within the “ClinicalTrials.gov” web site. The Primary and Secondary Endpoints (i.e., “Outcome Measures”) along with other required information for this study will be reported on ClinicalTrials.gov.

### 13.7 Descriptive factors

Age:  $\geq 70$  vs.  $< 70$

ECOG PS: 0-1 vs. 2

### 13.8 Inclusion of women and minorities

This study will be available to all eligible patients, regardless of race, gender, or ethnic origin. There is no information currently available regarding differential effects of this regimen in subsets defined by race, gender, or ethnicity, and there is no reason to expect such differences to exist. Therefore, although the planned analysis will, as always, look for differences in treatment effect based on racial and gender groupings, the sample size is not increased in order to provide additional power for subset analyses.

The geographical region served by the Alliance, has a population which includes approximately 18 % minorities. Based on national statistics involving similar meningiomas, we expect about 15 % of patients will be classified as minorities by race and about 60 % of patients will be women. Expected sizes of racial by gender subsets for patients to this study are shown in the following table. Note that these values are for the maximum number of patients (36) that we expect to accrue.

DOMESTIC PLANNED ENROLLMENT REPORT					
Racial Categories	Ethnic Categories				Total
	Not Hispanic or Latino		Hispanic or Latino		
	Female	Male	Female	Male	
American Indian/ Alaska Native					0
Asian	1				1
Native Hawaiian or Other Pacific Islander		1			1
Black or African American	1	1	1		3
White	17	10	2	2	31
More Than One Race					
Total	19	12	3	2	36

Ethnic Categories:	Hispanic or Latino – a person of Cuban, Mexican, Puerto Rican, South or Central American, or other Spanish culture or origin, regardless of race. The term “Spanish origin” can also be used in addition to “Hispanic or Latino.” Not Hispanic or Latino
Racial Categories:	American Indian or Alaskan Native – a person having origins in any of the original peoples of North, Central, or South America, and who maintains tribal affiliations or community attachment. Asian – a person having origins in any of the original peoples of the Far East, Southeast Asia, or the Indian subcontinent including, for example, Cambodia, China, India, Japan, Korea, Malaysia, Pakistan, the Philippine Islands, Thailand, and Vietnam. (Note: Individuals from the Philippine Islands have been recorded as Pacific Islanders in previous data collection strategies.) Black or African American – a person having origins in any of the black racial groups of Africa. Terms such as “Haitian” or “Negro” can be used in addition to “Black or African American.” Native Hawaiian or other Pacific Islander – a person having origins in any of the original peoples of Hawaii, Guam, Samoa, or other Pacific Islands. White – a person having origins in any of the original peoples of Europe, the Middle East, or North Africa.

#### 14.0 CORRELATIVE AND COMPANION STUDIES

There will be 1 substudy and all patients are encouraged to participate.

#### 14.1 Identification of blood and tissue-based molecular biomarkers (A071601-ST1)

##### 14.1.1 Background

Our goal is to identify blood and tissue-based molecular biomarkers of therapeutic response in patients with papillary craniopharyngioma tumors that are simultaneously treated with inhibitors of BRAF and MEK. Our group recently published a whole-exome and targeted sequencing study in craniopharyngiomas, where we identified recurrent BRAF mutations in papillary craniopharyngiomas and recurrent beta-catenin mutations in adamantinomatous craniopharyngiomas. The vast majority of papillary craniopharyngioma cases (~95%) harbored the oncogenic BRAF V600E mutation. In the correlative analyses for this clinical trial we propose to perform several genome wide analyses on craniopharyngioma samples. If normal patient DNA is available, we will perform whole exome sequencing on these samples. If normal patient DNA is unavailable we will perform targeted sequencing that is limited to roughly 500 cancer-associated genes. Transcriptome analysis will be performed on all samples where there is sufficient tissue. Common mechanisms of resistance have been reported in other cancers treated with BRAF/MEK inhibition. This data will help us to identify genetic biomarkers of response and of resistance. These studies could provide suggestions as to other therapies that might aid tumors that do not respond to BRAF and MEK inhibition. We will also perform pharmacodynamics studies prior to and after treatment using immunohistochemical analysis, to assess evidence of MAPK pathway activation pre- and post-treatment with vemurafenib + cobimetinib combination.

Furthermore, using an assay which has been well-validated in melanoma patients, we recently detected circulating BRAF V600E mutation in the blood of a patient with a papillary craniopharyngioma. We hope to validate the utility of this test through analysis of blood collected in this trial. We will assess whether the circulating BRAF V600E assay can be used to predict which patients have a papillary craniopharyngioma (i.e. ‘liquid

biopsy'), and whether the levels of circulating BRAF V600E correlates with response to therapy.

We also propose to perform either whole exome, transcriptome sequencing or targeted sequencing of 500 cancer associated genes on post-treatment resection samples – on either residual tissue samples that are resected following a successful initial course of treatment or on recurrence samples that regrow following termination of treatment or while on treatment. We hope to identify mechanisms of resistance in those samples.

We may also perform immunofluorescence characterization of tissue pre- and post-treatment using a range of markers to characterize cell cycle status, relevant cell signaling pathways, immune infiltrates and other possibly relevant markers as outlined below.

#### **14.1.2 Methods**

##### **Whole exome sequencing and analyses**

Whole exome sequencing will be performed following DNA fragmentation and purification and then library preparation with DNA barcoding. Read pairs will be aligned to the hg19 reference sequence and somatic variant calling will be performed within the Firehose environment and will be annotated to genes and compared to events in the Catalogue of Somatic Mutations in Cancer (COSMIC). Whole exome sequencing will allow us to determine: 1. If there are genetic markers that are associated with response or resistance to therapy and 2. To determine if treatment results in the evolution of a population of cells with a recurrent molecular genetic aberration that drives resistance.

##### **Transcriptome analyses**

Transcriptome sequencing will be performed using Illumina Tru Seq™ RNA Sample Preparation at the Broad Institute from FFPE tissue samples (fresh frozen tissue when available). This method uses oligo dT beads to select mRNA from the total RNA sample. The selected RNA is heat fragmented and randomly primed before cDNA synthesis from the RNA template. The resultant cDNA then goes through Illumina library prep (end repair, base 'A' addition, adapter ligation, and enrichment) using Broad designed indexed adapters for multiplexing. After enrichment, the samples will be qPCR quantified and equimolar pooled before proceeding to Illumina sequencing. RNA-seq analysis will be carried out using PRADA (Pipeline for RNA-Sequencing Data Analysis). Somatic variant, small deletions and insertion calling will be performed within the Firehose environment with the published caller algorithms. Transcriptome sequencing will allow us to determine if there is expression of genetic markers that are associated with response or resistance to therapy.

##### **Targeted sequencing and analyses**

Targeted sequencing of over 500 cancer associated genes will be performed on DNA that has been fragmented and used for library preparation with DNA barcoding. Read pairs will be aligned to the hg19 reference sequence and somatic variant calling will be performed within the Firehose environment and will be annotated to genes and compared to events in the Catalogue of Somatic Mutations in Cancer (COSMIC).

##### **Circulating DNA**

A highly-sensitive blood-based BRAF V600E mutation assay will be used to detect the mutation from the blood of patients with craniopharyngiomas. We used this assay to detect BRAF V600E from the blood of a patient with a papillary craniopharyngioma treated at our institution. This protocol starts with an RT-PCR reaction followed by digestions with TspR1, a restriction enzyme which preferentially digests the wild-type product but not the V600E mutated PCR product. A second, nested PCR using the digested material is carried

out. After a second digestion with TspR1, the product is then subjected to a real time PCR specific for the V600E mutation and not wild type sequences.

#### **14.1.3 Statistical considerations**

Due to small sample size, the primary objective of the analysis of all of the molecular correlatives is hypothesis generation and any significant findings would require additional research, testing and validation in an independent cohort.

As data permits, analyses of biomarkers will be summarized by descriptive statistics, including mean (standard deviation), median (range), and proportion (percentage) overall and per responders vs. non-responders.. Biomarkers will be compared between responders and non-responders with parametric or nonparametric techniques when it is appropriate. The association between biomarkers and time-to-event outcomes (e.g., OS, PFS) will be evaluated by Cox proportional hazards model. If the sample size permits, multivariable regression (Logistic regression for response endpoint and Cox model for OS/PFS) will be used to explore the relationship between these biomarkers measured at baseline and outcomes after adjusting for relevant covariates. Multiple comparison correction will be applied when it is necessary.

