### 1.3 Promising activity in case reports of patients with craniopharyngioma

We recently treated a patient who presented with multiply recurrent BRAF V600E craniopharyngioma using dabrafenib (150mg, orally twice daily) and trametinib (2mg, orally twice daily). After 35 days of treatment, tumor volume was reduced by 85%. Mutations that commonly mediate resistance to MAPK pathway inhibition were not detected in a post-treatment sample by whole exome sequencing. A blood-based BRAF V600E assay detected circulating BRAF V600E in the patient's blood. In another recently reported case, a patient with a multiply recurrent papillary craniopharyngioma treated with the BRAF inhibitor vemurafenib also had a dramatic tumor response. Given these promising and unique tumor responses, and the consistent occurrence of the BRAF V600E mutation in nearly all papillary craniopharyngiomas, we propose a Phase II study evaluating the combination of BRAF and MEK inhibition in patients with papillary craniopharyngiomas.

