#### 11.4.5.4 Evaluation of measurable lesions for central radiology review

Criteria for central radiology review is based on volumetric criteria that has been used in other brain tumors, including benign brain tumors.

- **Complete response (CR):** All of the following must be true:  
Disappearance of all measurable lesions on consecutive magnetic resonance imaging (MRI) or CT 4 weeks apart. No new lesions. No evidence of non-measurable disease. Lesions must be assessed using the same techniques at baseline. Neurologically/clinically stable or improved
- **Partial response (PR):**  
≥20% decrease under baseline in the volume of all measurable lesions. No progression of nonmeasurable disease. No new lesions. All measurable and non-measurable lesions and sites must be assessed using the same techniques as baseline. Neurologically/clinically stable or improved
- **Progression (PD):** At least one of the following must be true:  
> 20% increase in the volume of all measurable lesions using the same techniques as baseline, OR clear worsening of any nonmeasurable disease, OR appearance of any new lesion/site, OR clear clinical worsening or failure to return for evaluation due to death or deteriorating condition (unless clearly unrelated to this cancer)
- **Stable disease (SD):** Neither sufficient shrinkage to qualify for PR, nor sufficient increase to qualify for PD. Stable clinically

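### The biomarker analysis in Section 14.1.3 uses tumour response only as a yes/no status; adding percent change in central volume would use data already collected and be more sensitive (minor).

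*Combined protocol and SAP*

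**What the plan says.** Objective 2.4.1 is to evaluate molecular biomarkers of response. Section 14.1.3 gives the analysis. After descriptive summaries, overall and by response status, it states: "Biomarkers will be compared between responders and non-responders with parametric or nonparametric techniques when it is appropriate". For time-to-event data it states: "The association between biomarkers and time-to-event outcomes (e.g., OS, PFS) will be evaluated by Cox proportional hazards model". If numbers allow, multivariable models follow: "Logistic regression for response endpoint and Cox model for OS/PFS". It also states that "the primary objective of the analysis of all of the molecular correlatives is hypothesis generation".

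Section 14.1.3 does not define a responder. Section 13.2.1 does: CR or PR by central radiologic review. Section 11.4.5.4 sets the volumetric part of PR at a "20% decrease under baseline in the volume of all measurable lesions" or more, and adds conditions on new lesions, non-measurable disease and clinical status. Section 13.2.1 also has volumes assessed every 2 cycles. Relative change in tumour size is analysed by name only in Section 11.4.5.6, where volumetric and two-dimensional measurement are compared against patient outcomes. Biomarkers do not enter there.

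Section 14.1.1 asks whether circulating BRAF V600E levels correlate with response, without saying on what scale response is measured.

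**The concern.** Central review yields a percent volume change for each patient with a baseline and a follow-up scan. The biomarker plan reduces that to which side of one threshold the patient falls on. Differences in depth of response within each group are then lost to the analysis.

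The threshold is also shallow beside the activity cited in Section 1.3, where one patient is described thus: "After 35 days of treatment, tumor volume was reduced by 85" percent. If many patients respond deeply, variation in depth may say more about a biomarker than the count of patients above or below 20%.

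At stake is the sensitivity of an exploratory objective. The primary and secondary conclusions are not affected.

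**Working it through.** **Inputs.** 16 evaluable patients per cohort, 32 in all (13.3.1); null response rate 5% and alternative 30% (13.2.2); continue if at least 1 of 9 respond, success if at least 3 of 16 (13.2.3); PR threshold 20% (11.4.5.4). Section 14.1.3 states no power, error rate or effect size. My assumptions are a normally distributed outcome, a biomarker–outcome correlation of 0.5, one continuous biomarker, an uncorrected two-sided 5% test, and consent to the substudy by all evaluable patients.

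**Step 1. The plan's own design figures.** P(success) = Σ over x₁ = 1 to 9 of b(x₁; 9, p) × P(X₂ ≥ 3 − x₁), with X₂ ~ Bin(7, p). This gives 0.0406 at p = 0.05 and 0.8864 at p = 0.30. P(stop at stage 1) = (1 − p)⁹, which is 0.6302 and 0.0404. All four match the table in 13.2.2, so the planning rates can be used as printed.

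**Step 2. Information kept by the split.** For a normal outcome cut so that a share p are responders, relative efficiency is φ(z_p)² / [p(1 − p)].

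| Response rate | Efficiency | Lost |
|---|---|---|
| 50% | 0.3989² / 0.25 = 0.637 | 36% |
| 30% | 0.3477² / 0.21 = 0.576 | 42% |
| 20% or 80% | 0.2800² / 0.16 = 0.490 | 51% |
| 10% or 90% | 0.1755² / 0.09 = 0.342 | 66% |

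The loss passes one half only near or beyond 20% and 80%.

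**Step 3. Power.** I simulated bivariate normal data with correlation 0.5. Spearman correlation on the continuous outcome is compared with an exact Wilcoxon test after the split.

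| Response rate | n = 32: rank correlation | n = 32: split | n = 16: rank correlation | n = 16: split |
|---|---|---|---|---|
| 30% | 80% | 56% | 46% | 26% |
| 50% | 80% | 62% | 46% | 30% |
| 80% | 80% | 48% | 46% | 20% |
| 90% | 80% | 32% | 46% | about 11% |

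Repeat runs differ by about one percentage point: 79% to 80% for the rank correlation at n = 32, and 31% to 33% for the split at a 90% response rate.

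**Step 4. Group sizes.** Expected non-responders among 32 are 32 × 0.95 = 30.4 at the null rate, 32 × 0.70 = 22.4 at the alternative, and 32 × 0.10 = 3.2 at an assumed 90%. At 90%, P(2 or fewer non-responders) = 0.37. With a single non-responder among 32, the smallest two-sided exact Wilcoxon p-value is 2/32 = 0.0625, so 5% cannot be reached.

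**The case against.** The strongest reply is that this is a preference about method in an optional substudy that claims no power and calls itself hypothesis-generating. Section 14.1.3 makes its analyses conditional on what the data and sample size allow. Its list of time-to-event outcomes is open-ended, and Section 14.1.1 leaves room for a correlation with depth of response. This limits the severity. It does not supply the missing analysis, because no sentence in 14.1.3 names a continuous response outcome.

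The gain is also idealised. Much of the substudy is mutation calling, where a marker is present or absent, and the rank-correlation figures do not carry over directly. A panel of about 500 genes makes a single uncorrected 5% test unrepresentative. Percent change cannot go below −100% and may bunch there. Within one cohort of 16, even the continuous analysis reaches only about 46%. All of this stands: the power figures show direction and rough size, not what the substudy will achieve.

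Percent volume change also has a cost. It ignores new lesions, non-measurable progression and clinical worsening, and it is missing for a patient who dies or deteriorates before a follow-up scan. That too stands, and is why the responder comparison should be kept.

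A reader might go further and infer that most of the response information is lost. At the 30% design alternative the loss is 42%, under half. A reader might infer that there will be almost no non-responders. The planning rates imply 22 to 30 of 32, with responders the scarce group; a rate near 90% is stated nowhere, and Section 1.3 offers two case reports without a denominator. A reader might infer that logistic regression must separate with one to three non-responders. For one continuous biomarker with no association, separation needs all of them at one extreme: probability 2/32 = 6%, 2/496 = 0.4% and 2/4960 = 0.04% for one, two and three.

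**Conclusion.** The point holds in a limited form. Apart from time-to-event outcomes, 14.1.3 relates biomarkers to response only as a binary status, while the continuous measure behind that status is already collected. Under the stated assumptions the split costs 36% to 42% of the information at response rates between 30% and 50%, and more than half at about 20% or below and 80% or above. At the design alternative, power is about 80% against 56% for 32 patients, and about 46% against 26% for 16. If the response rate reached about 90%, which is an assumption and not a planning figure, about 3 of 32 patients would be non-responders and the split would have roughly 31% to 33% power.

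These sizes rest on a normal outcome, a correlation of 0.5, continuous biomarkers, no multiplicity correction and full uptake. Lower uptake would reduce power for both methods. Severity is minor: the affected objective is exploratory, and the remedy is an addition to the planned comparison.

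**What to change.** In Section 14.1.3 add, alongside the responder/non-responder comparison, the association of each biomarker with best percent change from baseline in centrally measured tumour volume during the first four cycles, by rank correlation or linear model, stratified by cohort. State that patients with PD by new lesion, clinical worsening or death and no follow-up volume are ranked as the worst outcome, so that failures are not dropped. This rule suits the rank method; a linear model would be limited to patients with a measured change, and the text should say so. Keep the hypothesis-generating label.

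The cost is a few sentences of text. No new samples, scans or central reads are needed. The downside is that percent volume change leaves out the non-volumetric conditions for response, which the retained responder comparison covers.

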**APPENDIX I: REGISTRATION FATIGUE/UNISCALE ASSESSMENTS****Registration Fatigue/Uniscale Assessments**

At patient registration, this form is to be administered by a nurse/CRA, completed by the patient, and entered into Medidata Rave at the time of registration.

If needed, this appendix can be adapted to use as a source document. A booklet containing this assessment does not exist – please do not order this booklet.

How would you describe:

your level of fatigue, on the average in the past week including today?

0	1	2	3	4	5	6	7	8	9	10
No										Fatigue
Fatigue										as bad
										as it can be

your overall quality of life in the past week including today?

0	1	2	3	4	5	6	7	8	9	10
As bad as										As good as
it can be										it can be

